For the nested cohort component, we will exclude adults who have no documented evidence of HIV infection or a NCD of interest. We will also exclude people who did not participate in the baseline patient survey, are not likely to remain at the site for their care through the end of cohort follow-up, or unwilling/ unable to provide written informed consent.

We will exclude any potential IDI, FGD/ implementation survey, or KII participant if they are unwilling or unable to provide written informed consent.

iv. Justification of exclusion of any sub-segment of the population

We will not exclude any sub-segment of the adult population for the cross-sectional patient surveys. We have chosen to exclude infants, children, and adolescents under 18 years of age from this analysis as the mechanisms and systems built to support their care are unique, and because this population has a lower risk of cardio-metabolic complications of HIV.

v. Site sampling and randomization, including sample size and statistical power

The pilot sites for the formative evaluation will be selected based on their feasibility to deliver TASKPEN and to reflect different levels of the health system. For the mini stepped wedge study, the pilot sites will be Chilenje 1st level hospital and George urban health centre, subject to approval by our TAC and findings from our formative assessment. We will use a computer-generated allocation algorithm to randomize the time at which Chilenje and George will switch from standard of care to the TASKPEN intervention. This timing will be concealed from clusters and the trial team until ~4 weeks before the switch date.

Table 4. Study sites for the TASKPEN formative assessment.

Facility	Annual PLHIV (TX_CUI	% of TX_ clients with documented (within last 6 m	pressure measu	Avg. No. d	Health Level	Integration of NCD a care
Mtendere	6138	727 (11.84%)	719 (11.71%)	833	First	Partial integration (ART services available in outpatient department)
Chawama	10161	5599 (55.10%)	4485 (44.14%)	1353	Secondary	No integration
Chilenje	8083	7225 (89%)	6484 (80%)	1045	First	No integration
George	8785	1103 (13%)	38 (0.4)	1345	Primary	No integration

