For the cross-sectional patient surveys, we will survey a consecutive sample of 188 eligible patients in care at each clinic at each of the 3-time points (i.e., baseline, midline, and end-line) using a stepped-wedge cluster-randomized design. Applying this design with a sample of 2 clusters (i.e., sites), 3 survey time points, 2 steps, 1 cluster switching from control to intervention at each step, and an average of 564 subjects per cluster (i.e., 188 participants per cluster per period) achieves 80% power to detect a risk ratio of 1.25 (for the risk of dual HIV/NCD control during the intervention period compared to the control period) at the 0.05 significance level with an inter-class correlation coefficient of 0.25. We assumed that

the proportion of participants achieving dual HIV/NCD control is 0.75 under the alternative hypothesis, and 0.6 under the null hypothesis, and used the two-sided Wald Z-Test as the test statistic. Based on the above calculation, we will survey 564 eligible patients at each clinic across the 3-time points (i.e., 3*188=564 eligible patients) to achieve **a total sample size of 1128 participants** for the mini stepped-wedge. It is important to note that participants previously surveyed will not be eligible for subsequent surveys—i.e., once interviewed, a patient should not be eligible for interview in subsequent surveys unless they are part of the nestd cohort. Finally, as part of the baseline, midline, and endline cross-sectional surveys, we will review de-identified routine data for all PLHIV in care at the study sites during the study period to estimate HIV viral load completeness, NCD-variable data completeness (e.g., routine weight and blood pressure measurements), and performance on WHO PEN indicators in the routine medical record.

For the nested cohort component, the total sample size of ~200 participants was selected for operational feasibility and to assess our ability to collect longitudinal cardio-metabolic data, but does not involve *a priori* hypothesis testing.

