For qualitative data, final qualitative transcripts will be reviewed for accuracy against original notes and recordings, for at least 5% of the transcripts. Any errors will be corrected by the person who conducted the interview using good clinical practice (GCP) correction procedures. Monitoring visits will be conducted on an ad hoc basis to ensure that data collection is being done well. Any retraining will be done on-site on an as-needed basis, to ensure that collected data are of high quality.

iv. Data ownership, sharing and governance

All study data will be owned by the Zambia Ministry of Health (MOH) as the stewards of the national HIV program. As the owners of the data, the Zambia MOH will ultimately be responsible for oversight of all data governance issues. Qualitative data will not be shared due to the small sample size involved and the potential for deduction. All decisions regarding data dissemination, for example at the request of a journal at the time of publication, will be made by the Zambia MOH as the owners of the data.

g. Data analysis

i. Quantitative data analysis

We will summarize background characteristics (for participants and facility) by the intervention periods (control, intervention). The preliminary effect of the TASKPEN intervention will be estimated by comparisons of the percentage of participants in the patient surveys with dual HIV/NCD control during the control period and the intervention period. We will also calculate CVD risk score based on the ASCVD, D.A.D, or similar and compare this outcome between the control and intervention periods. Binary outcomes will be analysed using generalized linear mixed logistic model with margins to estimate risk ratio and risk difference adjusted for key potential confounders. Health facilities will be specified as random effects while time will be specified as fixed effect in the model. Continuous outcomes will be analysed using linear models to estimate mean score difference in an analogous way.

Quality of life score will be analysed in a similar way. P-values less than 0.05 will be considered statistically significant. We do not plan to impute missing values. All analyses will be performed using Stata 16 MP4 (StataCorp, College Station, TX, USA).

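### With only two purposively chosen sites, a random site effect lets part of the site difference into the TASKPEN estimate; a fixed site term avoids this

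*Combined protocol and SAP*

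**What the plan says.** Under Specific Objective #2, the quantitative part of the data analysis section (g.i) compares dual HIV/NCD control between control and intervention periods. It uses a mixed logistic model with margins, adjusted for key potential confounders, and treats p below 0.05 as significant. On the site and time terms it says: "Health facilities will be specified as random effects while time will be specified as fixed effect in the model". Continuous outcomes follow by analogy. A later paragraph of the same section adds a sandwich or resampling variance for differences and ratios, to reflect clustering by site.

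The sample size section (d.v) describes a design "with a sample of 2 clusters (i.e., sites), 3 survey time points, 2 steps", with 188 participants per site per survey. It "achieves 80% power to detect a risk ratio of 1.25" "at the 0.05 significance level with an inter-class correlation coefficient of 0.25". It assumes that "the proportion of participants achieving dual HIV/NCD control is 0.75 under the alternative hypothesis, and 0.6 under the null hypothesis", and says the authors "used the two-sided Wald Z-Test as the test statistic".

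The sites are not a random sample of facilities. Subject to approval by the advisory committee, "the pilot sites will be Chilenje 1st level hospital and George urban health centre". Section d.v says they are selected for feasibility of delivery and to represent different levels of the health system, and Table 4 lists one as first level and the other as primary. Which of the two switches first is randomised.

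The plan gives no small-cluster correction, no fixed-site alternative, and no rule for a site variance estimated at zero.

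**The concern.** A random intercept works by estimating how much sites vary and then deciding how far to correct for the site difference. With two sites that estimate has a single contrast behind it, and maximum likelihood pulls it towards zero. If it reaches zero, the model treats the two facilities as exchangeable, and the effect is read from the raw midline difference between a first-level hospital and a primary health centre. If it is positive but small, only part of the difference is removed. This needs no site-by-period variation and no heterogeneity of effect.

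The preliminary effect is among the pilot's primary measures (outcomes section), and the study design section says it is to help plan the larger trial. A shifted estimate with too small a standard error would carry into that planning.

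**Working it through.** **1. Reproduce the plan's power.** Inputs from section d.v: 2 sites, 3 surveys, m = 188 per cell, p0 = 0.60, p1 = 0.75, ICC = 0.25, two-sided 0.05 Wald Z. The standard stepped-wedge variance for this layout is

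Var = 2·s²·(s² + 3τ²)/(s² + 2τ²), with s² the cell variance and τ² the site variance.

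Take s² = p0(1−p0)(1−ICC)/m = 0.24 × 0.75/188 = 0.000957 and τ² = 0.25 × 0.24 = 0.06. Then Var = 0.002865, SE = 0.0535, and power = Φ(0.15/0.0535 − 1.96) = 80.0%. The stated figure reproduces, and Var/s² = 2.99. Other conventions for the individual variance give 68% to 89%.

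**2. How the random-site estimate is built.** Let D1, D2, D3 be the observed differences (early-switching minus late-switching site) at baseline, midline and endline. With survey fixed, the linear version of the model gives

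estimate = D2 − w·(D1 + D3), with w = τ²/(s² + 2τ²).

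- Site variance estimated at zero: w = 0, so the estimate is D2, with variance 2s². The whole site difference is in it.
- Fixed site indicator: w = 1/2, so the estimate is D2 − (D1 + D3)/2, with variance 3s². The site difference cancels.

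**3. When the variance collapses.** For small site differences the individual variance is close to 0.24, so s² = 0.24/188 and √s² = 3.6 points. Maximum likelihood sets the site variance to zero when the average of D1 and D3 is smaller in size than √(3s²) = 6.2 points. That average has standard error 3.6 points. For a true difference d, the collapse probability is therefore Φ(√3 − d/√s²) − Φ(−√3 − d/√s²): 92% at d = 0, 63% at 5 points, 41% at 7, 14% at 10, under 1% at 15.

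**4. Type I error.** No TASKPEN effect, control rate 0.60, 188 per cell. The site difference d is an **assumption**, because the documents give none. The mixed logistic columns come from 2,500 simulated trials per row (adaptive quadrature, Wald test). The other columns are large-sample normal calculations.

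| d (points) | Mixed logistic, random site | Mixed logistic: variance at zero | Normal ML | Normal REML-type | Logistic, fixed site |
|---|---|---|---|---|---|
| 0 | 4.5% | 92% | 5.3% | 5.7% | 4.6% |
| 5 | 11.2% | 64% | 12.8% | 9.5% | 4.9% |
| 7 | 13.3% | 40% | 15.8% | 10.1% | 5.8% |
| 8 | 12.6% | 30% | 16.2% | 9.7% | 5.2% |
| 10 | 11.5% | 14% | 14.8% | 8.5% | 4.9% |
| 15 | not run | not run | 8.7% | 6.3% | not run |
| 20 | not run | not run | 6.6% | 5.5% | not run |

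A separate REML-type check peaked near 11%. In the normal ML calculation the estimate moves towards the site difference by 3.2 points at d = 5, 3.5 at d = 7 and 3.1 at d = 10. The REML-type shift is about 1.4 to 1.8 points over the same range. The fixed-site estimate does not move.

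**5. At the protocol's ICC.** Drawing site effects at random with ICC 0.25, the variance collapses in 14–15% of trials and the error is 5.6% (mixed logistic) to 7.7% (normal ML). With ICC 0.01 to 0.05 the error is 8% to 11%. Fixed-site error in the same simulations is 4.0% to 5.2%.

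**6. Precision with a fixed site term.** Var = 3s², against 2.99s² in the plan's formula. With the (1−ICC) factor, SE = √(3 × 0.000957) = 0.0536 and power is 79.9%. Without it, s² = 0.24/188 gives SE 0.0619 and power 68%. Averaging the variances at 0.60 and 0.75 (0.21375) gives SE 0.0584 and power 73%. Simulation gave 67% to 72%.

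**The case against.** Several points on the other side are sound.

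- **Size depends on the site difference.** The inflation belongs to moderate differences. ICC 0.25 at a rate of 0.60 implies a site SD of about 24 points and a median difference between two sites of about 23 points (0.6745 × √(2 × 0.06)), where the problem has nearly faded. A reader might infer that the variance usually collapses and that 15% error is to be expected. On the plan's own ICC that does not follow, and the 15–16% figures come only from the normal approximation.
- **Bias.** A reader might infer that the estimate is biased by whatever difference exists between the facilities. It is not: large differences are mostly removed, and because the switch order is randomised the shift can take either sign. It is a bias conditional on the realised order, or extra variance over the randomisation. But the trial will have only one realised order.
- **The written plan has more in it.** It adjusts for confounders and mentions sandwich or resampling variance, neither of which was simulated. Covariates could narrow the site difference. A sandwich variance changes the standard error, not the shift, and also rests on two clusters.
- **The effect is called preliminary.** That lowers the stakes, but section d.v still powers a 0.05 test on it.

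Table 4 shows very different completeness of routine measurements at the two sites (89% and 80% against 13% and 0.4%). That is documentation, not dual control, so it cannot supply the missing site difference.

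**Conclusion.** The concern holds in a bounded form. Modelling two purposively chosen sites as random makes the TASKPEN estimate depend on a variance that two units cannot support. The error of the 5% test is near nominal for equal sites, about 11–13% in the mixed logistic model for assumed differences of 5 to 10 points, and about 6–7% by 20 points in the normal ML calculation. At the protocol's ICC of 0.25 it averages about 6–8%, with collapse in about one trial in seven. A fixed site term gives about 4–6% throughout and no shift. These figures assume a constant effect, no site-by-period variation, no covariates and a model-based Wald test.

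A reader might also infer that the change costs no planned precision. That is true only while the (1−ICC) factor at ICC 0.25 is kept. Site differences of 5 to 10 points correspond to an ICC of about 0.005 to 0.02 (d²/2 divided by 0.24). There the factor is close to 1 and power is about 68–73%. This shortfall comes from the power inputs and not from the choice of a fixed site term, but it should be stated.

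**What to change.** In section g.i, replace the sentence on random facility effects with a model that has site as a fixed indicator, survey (baseline, midline, endline) as a fixed factor, and one TASKPEN term. Obtain the risk ratio and risk difference by margins from that model. Use the same terms for the continuous outcomes.

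In section d.v, add that the 80% power uses an individual variance of p0(1−p0)(1−ICC) with ICC 0.25, and that fixed-site power at 188 per cell is about 68–73% without that factor.

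Cost: two short text changes and no new data. The standard error is up to √(3/2) = 1.22 times what the random-site model would report when it sets the site variance to zero, but essentially equal to what the sample size formula assumes. Inference then refers to these two sites, which suits a purposive pilot.

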By completing specific objective #1, we will be fully prepared for TASKPEN pilot testing, having ready an adapted version of TASKPEN that includes all the essential implementation strategies necessary to overcome barriers to HIV-NCD integration in routine care settings. While the peripheral elements and implementation strategies used to introduce TASKPEN may undergo adaptation under specific objective #1, it is important to note that the 5 core, evidence-based components outlined in Table 1 and proposed for this pilot will not substantively change. Under specific objective #2, we will launch the TASKPEN pilot and fully task-shift our intervention to NPHWs and integrate it within the PEPFAR-supported HIV service delivery platform. Concurrently with implementation, during the pilot we will identify facilitators and barriers to TASKPEN introduction, assess preliminary implementation outcomes and patient and provider preferences related to integrated management of cardio-metabolic complications for PLHIV, ascertain early clinical outcomes for patients before and after TASKPEN piloting, and collect formative costing data.

b. Study design

For this objective, we will conduct a quasiexperimental "mini" cross-sectional stepped-wedge study at the 2 pilot sites employing a mixed methods approach. First, at the two pilot sites (i.e. A and B), we will conduct a baseline assessment of select outcomes for PLHIV receiving the existing standard of care. This will involve conducting a brief biobehavioural survey or "patient survey" among a consecutive sample of ~376 adult PLHIV presenting for routine HIV services at the two sites (i.e., ~188 PLHIV per site, see Sample Size and Statistical Power below). After this first patient survey, one randomly selected facility (i.e. cluster) will be switched to the full TASKPEN intervention. The patient survey will be repeated again with another ~376 adult PLHIV after ~3 months at both sites before switching the second site to the full TASKPEN intervention. After switching the second

Figure: Study schematic with "mini" stepped wedge and nested cohort.

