Using baseline, midline, and endline patient survey data and routine EMR data, we will assess the implementation outcomes described in Table 6. We will calculate standardized scores for validated instruments in our implementation survey. Comparisons of proportions for the aforementioned implementation outcomes will be done by calculating prevalence ratios and associated 95% confidence intervals as appropriate. Comparisons of continuous outcomes will be done by the Z-test/ 2-sample T-test or the Wilcoxon Rank-Sum test as appropriate.

To understand patient-level outcome measures of **disease control, retention**, **adherence**, and **viral suppression**, we will analyse data from the patient surveys. We will estimate **dual disease control** as the proportion of participants in the intervention and control periods who have a HIV viral load <200 copies/ml and do not have uncontrolled systolic hypertension, diabetes, and/or dyslipidaemia. We will calculate **retention** as the proportion of participants considered to be consistently engaged in care at 6 months according to the national HIV treatment program definition (e.g., without evidence of death, default, or loss to follow up defined as ≥30 days having elapsed since a missed pharmacy refill/ clinic visit). We will measure **adherence** in the nested cohort by reviewing pharmacy records at 6 months to calculate the medication possession ratio (MPR) over that time frame for anti-hypertensive, diabetes, and dyslipidaemia medications, as well as antiretroviral therapy. We will calculate **viral suppression** as the proportion of survey participants meeting established thresholds of suppression (e.g., viral load <1,000 copies/ml or <200 copies/ml) at 6 months following ART initiation and/or study enrolment. To compare outcome measures, we will report differences and ratios with accompanying 95% confidence intervals. We will compute variance for differences and ratios using the sandwich variance estimator or appropriate resampling approaches to account for the clustered nature of the data by site.

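### The data analysis section gives two conflicting recipes; read literally, the second compares control and intervention periods without site or calendar-time terms in the estimate

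*Combined protocol and SAP*

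**What the plan says.** All of this is in the combined protocol and SAP, section 8, Specific Objective #2, part g (Data analysis), item i (Quantitative data analysis), unless stated.

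- **First recipe (opening paragraph).** The preliminary TASKPEN effect is the control-period versus intervention-period comparison of dual control in the patient surveys. Binary outcomes get a mixed logistic model with margins for the risk ratio and risk difference: "Health facilities will be specified as random effects while time will be specified as fixed effect in the model". Continuous outcomes get an analogous linear model.
- **Second recipe (the next two paragraphs).** For implementation outcomes: "Comparisons of proportions for the aforementioned implementation outcomes will be done by calculating prevalence ratios and associated 95% confidence intervals as appropriate". Continuous outcomes are compared by Z-test, two-sample t-test or Wilcoxon rank-sum test. Dual control is estimated again, "as the proportion of participants in the intervention and control periods". Then: "To compare outcome measures, we will report differences and ratios with accompanying 95% confidence intervals". Clustering by site enters through a sandwich or resampling variance. No site or time term for the point estimate is named.
- **Design (part d.v).** "2 clusters (i.e., sites), 3 survey time points, 2 steps, 1 cluster switching from control to intervention at each step", with "an average of 564 subjects per cluster (i.e., 188 participants per cluster per period"). The order is drawn at random (part b): "After this first patient survey, one randomly selected facility (i.e. cluster) will be switched to the full TASKPEN intervention".
- **Routine records (part d.v).** Completeness of routine blood pressure and weight data is to be estimated alongside each of the three surveys. Table 4 gives 6484 of 8083 (80%) at Chilenje and 38 of 8785 (0.4%) at George, the tentative pilot pair.

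**The concern.** The two recipes do not give the same answer. In a stepped wedge the intervention periods are later by construction. With only two sites, each condition also draws twice as many cells from one site as from the other. A model with site and round terms separates these from the intervention effect; a period proportion, ratio or two-sample test does not. A sandwich or resampling variance alters the width of the interval, not its centre, and here it would rest on two clusters.

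Dual control is covered by both recipes, so an analyst could report either result as the preliminary effect. Part b says the survey data will supply the pilot effect size for planning the larger trial. The wrong recipe could therefore pass on a figure that partly reflects which site was drawn first.

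**Working it through.** **1. Reproduce the planned power.** Inputs from part d.v: 0.60 versus 0.75, ICC 0.25, two-sided 0.05 Wald Z, 188 per site per round. Take the Hussey-Hughes variance with a site random effect and period fixed effects.

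- Total variance 0.60 × 0.40 = 0.24, so τ² = 0.25 × 0.24 = 0.06 and the residual variance is 0.18. Per cell, σ² = 0.18/188 = 0.000957.
- I = 2, T = 3, U = 3, W = 0² + 1² + 2² = 5, V = 2² + 1² = 5.
- Var = Iσ²(σ² + Tτ²) / [(IU − W)σ² + (U² + ITU − TW − IV)τ²] = 2 × 0.000957 × 0.18096 / [0.000957 + 2 × 0.06] = 0.002865, so SE = 0.0535.
- Power = Φ(0.15/0.0535 − 1.96) = Φ(0.84) = 0.80.

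The claim that the design "achieves 80% power to detect a risk ratio of 1.25" therefore reproduces under a model with site and period terms. Other variance conventions at the same ICC give 0.68 to 0.89.

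**2. What a literal period contrast estimates under no effect.** Let A be the first site to switch (control, intervention, intervention) and B the second (control, control, intervention), with equal cells.

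- Control = (A + 2B)/3; intervention = (2A + B)/3.
- Difference = (A − B)/3, one third of the site gap.
- Ratio = (2A + B)/(A + 2B). Without a time trend this cannot leave the range 0.5 to 2.0.
- Mean round: control (1 + 1 + 2)/3 = 1.33; intervention (2 + 3 + 3)/3 = 2.67. The gap is 1.33 rounds of about 3 months, so about 4 months.

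**3. Dual control.** The documents give no site-level rates, so these are illustrations.

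- At ICC 0.25, between-site SD = √0.06 = 0.245. For two normally distributed site rates, the expected absolute gap is 2 × 0.245/√π = 0.276, and one third is 0.092.
- At ICC 0.05: SD = √(0.05 × 0.24) = 0.110; gap 0.124; one third 0.041.
- The planned difference is 0.75 − 0.60 = 0.15.

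| Assumed site rates | Ratio under no effect, higher site first | Lower site first |
|---|---|---|
| 65% / 55% | 1.06 | 0.95 |
| 70% / 50% | 1.12 | 0.89 |
| 80% / 40% | 1.25 | 0.80 |

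For trend alone, with both sites starting at 60% and rising 5 points per round: control (60 + 60 + 65)/3 = 61.7%, intervention (65 + 70 + 70)/3 = 68.3%, ratio 1.11. At 10 points per round it is 1.21.

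**4. The extreme case: routine blood pressure documentation.** Chilenje 6484/8083 = 80.2%; George 38/8785 = 0.43%.

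- Chilenje first: control (80.2 + 2 × 0.43)/3 = 27.0%; intervention (2 × 80.2 + 0.43)/3 = 53.6%; ratio 1.98.
- George first: the two swap; ratio 0.50.
- Weighted by Table 4 patient numbers: 2.04 and 0.49.
- The other documentation column, 7225/8083 = 89.4% and 1103/8785 = 12.6%, gives 1.67 and 0.60.

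**5. What site and round terms do.** In 500 null simulations per scenario, with 188 per cell, a logistic model with site and period as fixed effects stood in for the plan's mixed model.

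- At 89%/13% and at an assumed 70%/50%, the adjusted ratio centred on about 1.00, with 4% to 6% rejection.
- Unadjusted binomial intervals on the period ratio excluded 1 in 100% and about 64% of those null runs. These intervals ignore clustering, so the percentages do not carry over to a sandwich interval; the shift in the estimate does.
- At 80%/0.4% the adjusted ratio centred near 1 (1.02 or 0.98) but ranged from about 0.56 to 4.8, or 0.21 to 1.8 in the other order.

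**The case against.** The best defence is that the first recipe already governs. It covers binary outcomes without restriction, names dual control as the preliminary effect, and yields the same quantities (risk ratio and difference) that the later paragraph reports. The later paragraph can be read as defining outcomes, and a sandwich variance is compatible with model-based margins. The power figure also presumes site and period terms. Nowhere does the plan say pooled, crude or unadjusted.

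Much of this stands. A reader might infer that the plan has no site- or time-adjusted analysis, or that it commits to a crude ratio for the effect passed to the larger trial. The documents do not support either: the adjusted model is there, and dual control is assigned to it. What remains is that dual control then appears a second time under different wording, and that the two-sample tests, as named, have no place for site or time terms and contradict the linear model.

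Two further points also stand. The legible time points in the implementation outcomes table are about 6 months, when both sites have switched, and the provider surveys follow exposure at both sites. Those outcomes may have no control period, and the prevalence-ratio sentence does not name the groups compared. Retention and viral suppression are likewise defined at 6 months rather than by period. Routine blood pressure completeness is only said to be estimated; no passage commits to a control-versus-intervention ratio for it.

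**Conclusion.** The point holds as an unresolved conflict between two analysis recipes. Any comparison made literally between control and intervention periods under the second is confounded by one third of the site gap and about 4 months of trend. That follows from the design, given roughly equal cells.

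The size depends on the outcome. For dual control it is unknown from the documents. The 9-point and 4-point figures treat the ICC as true between-site variance with normally distributed site rates, and apply only if the mixed model is set aside. A reader might take ratios of 2.0 or 0.5 as typical of the plan. They are the limit of this design without a trend, reached by one routine-record indicator, and only if it were compared this way. That figure also rests on a tentative site pair and on reading a partly legible Table 4 column header as blood pressure.

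**What to change.** In the paragraphs on implementation and patient-level outcomes, state that every control-versus-intervention comparison of a survey or routine-record outcome uses the model in the opening paragraph with site and survey-round terms, reporting the marginal ratio and difference. Replace the two-sample tests with the analogous linear model for such comparisons. Show crude proportions only by site and round.

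For routine documentation indicators with extreme site gaps, report each site's change by round. At 188 per cell the adjusted ratio is too imprecise to use. The routine review covers all patients in care, which would narrow it considerably, but one ratio would still describe the two sites poorly: a site at 80.2% can rise by a factor of at most 1/0.802 = 1.25, while a site at 0.4% has no such ceiling.

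Report outcomes measured only at about 6 months, after both sites have switched, descriptively.

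The cost is wording and reuse of model code already planned, with somewhat wider intervals than the crude ones. The sample size need not change, since the stated power reproduces under site and period terms.
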